8.5. Randomization

Following screening, patients meeting all eligibility criteria will be enrolled in the study. Patients will be randomized via IWRS in a 1:1 ratio to receive either fosmetpantotenate or placebo during the 24-week double-blind period, followed by open-label treatment with fosmetpantotenate. Randomization will be stratified by weight (≥ 40 kg, ≥ 20 kg but < 40 kg, or < 20 kg) and age group (pediatric: ages 6 to < 18 years, or adult: ages 18 to 65 years, inclusive) as measured at the Screening visit.

For the open-label period, all patients will receive fosmetpantotenate open-label.

The IWRS will also randomize patients to one of the sampling schemes for PK sampling as described in [Section 9.4](#).

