12.9. Efficacy

12.9.1. Double-Blind Period

The primary efficacy analysis will be based on the FAS population defined for the double-blind period of the study (see [Section 12.3](#)). For each patient, the change from Baseline in PKAN-ADL scores at Weeks 3, 6, 12, 18, and 24 of the double-blind period will be used for analysis. The treatment effect will be evaluated on the basis of mixed model for repeated measures (MMRM) analysis to assess data from all visits simultaneously. The model will include fixed effects for treatment, age stratum (6 to <18 or 18 to 65 years), visit and treatment by-visit interaction, a random effect for patient within treatment group, and Baseline

PKAN-ADL score as a covariate. The PKAN-ADL measurement obtained prior to the first dose of investigational product will serve as each patient's Baseline value. Least-squares adjusted means and the adjusted mean difference between treatment groups will be reported at each study visit, along with 2-sided 95% confidence intervals (CIs) and the p-value for the treatment comparison.

The mixed-effect linear model will be implemented using PROC MIXED in SAS with the restricted maximum likelihood (REML) estimation method and Kenward-Roger degrees of freedom algorithm for the F-test. Significance tests will be based on least squares means using Type III sum of squares.

To support the primary efficacy analysis, analysis of covariance (ANCOVA) models will be applied to change from Baseline in PKAN-ADL scores assessed after 3, 6, 12, 18, and 24 weeks of treatment. For each week analyzed, the model will include treatment and age stratum (6 to <18 or 18 to 65 years) as fixed effects and Baseline PKAN-ADL score as a covariate. Estimates of the adjusted mean treatment differences and the 2-sided 95% CIs at each time point will be obtained from the model.

Secondary and exploratory efficacy endpoints that are continuous measures recorded at each study visit will be evaluated using the MMRM approach described above for the primary efficacy endpoint. Summary statistics for efficacy measures will include graphical plots of mean and mean change from Baseline values at each study visit, by treatment group.

Treatment effects on categorical outcomes will be examined using frequency tables and tested using Cochran-Mantel-Haenszel chi-square methods with stratification by age group (6 to <18 or 18 to 65 years).

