2.7 Pharmacogenomics

Pharmacogenomic assessment may be performed on blood samples drawn at screening for drug metabolizing enzymes, transporters, or indicators of therapeutic response or safety. These assessments will only be performed where local regulations permit and where approved by the site's Institutional Review Board/Independent Ethics Committee (IRB/IEC), and will be subject to separate consent/assent by the patient/parent/legal guardian as appropriate.

3 Overall Study Design

This is a pivotal, randomized, double-blind, placebo-controlled, multi-center, 2-arm study evaluating 24 weeks of treatment with fosmetpantotenate or placebo in patients with PKAN aged 6 to 65 years, with a 278 week open-label extension.

Eligible patients will be randomized in a 1:1 ratio to receive either fosmetpantotenate or placebo for a 24-week double-blind period; randomization will be stratified by screening weight and age group (pediatric, adult), as reported by Interactive Web Response System (IWRS). In Protocol Version 1, Pediatric is defined as ' <19 ' and Adult is defined as ' ≥ 19 .' In subsequent versions of the Protocol, Pediatric is defined as ' <18 ' and Adult is defined as ' ≥ 18 '.

Treatment in the double-blind period will begin with dose escalation for Days 1-3, followed by the full dose 3 times daily (TID) starting on Day 4. Matching placebo will be given according to the same dose escalation sequence as active investigational product. Study visits during the double-blind period are scheduled at baseline (within 1 to 2 days prior to the start of the double-blind treatment), Days 1 through 4, and Weeks 3, 6, 12, 18, and 24. See Protocol Appendix A ([Table 15.1-1](#)) for the schedule of assessments performed during the double-blind period.

After completing the double-blind period, patients will be eligible to receive open-label fosmetpantotenate for up to 278 weeks. During the open-label period, study visits are scheduled at Weeks 27, 30, 36, 48, 60, 72, 84, 96, 108, 120, 146, 172, 198, 224, 250, 276, and 302. See Protocol Appendix A ([Table 15.1-2](#)) for the schedule of assessments performed during the open-label period.

In total, patients will be in the study for approximately 302 weeks, with 24 weeks in the randomized, double-blind treatment period and 278 weeks in the open-label period.

4 Statistical Methodology

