Figures will be presented which show the PKAN-ADL total score for each visit during the double-blind period, as well as change from baseline score, by treatment group. This will be run using the Double-Blind FAS and repeated using the PPS.

In addition, a by-patient listing will be provided, which presents PKAN-ADL scores (total and for each item) across all assessments in the double-blind and open-label periods for patients in the Double-Blind FAS.

The change from baseline in PKAN-ADL total scores will be used to test the following hypotheses:

Null hypothesis:

There is no difference between the fosmetpantotenate and placebo groups, as measured by the change in PKAN-ADL total score from baseline to the end of the 24-week double-blind treatment period, with adjustment for age group and baseline PKAN-ADL total score.

Alternate hypothesis:

There is a difference between the fosmetpantotenate and placebo groups, as measured by the change in PKAN-ADL total score from baseline to the end of the 24 week double-blind treatment period, with adjustment for age group and baseline PKAN-ADL total score.

That is:

H_0 : Change from baseline PKAN-ADL Total Score at Week 24 (fosmetpantotenate) = Change from baseline PKAN-ADL Total Score at Week 24 (Placebo) *estimated via repeated measure analysis, with adjustment for age group and baseline score*

H_1 : Change from baseline PKAN-ADL Total Score at Week 24 (fosmetpantotenate) \neq Change from baseline PKAN-ADL Total Score at Week 24 (Placebo) *estimated via repeated measure analysis, with adjustment for age group and baseline score*

The primary efficacy analysis will be based on the FAS population in the double-blind period of the study. For each patient, the change from baseline in PKAN-ADL total scores at Weeks 3, 6, 12, 18, and 24 of the double-blind period will be used for analysis. The treatment effect will be evaluated on the basis of a mixed model for repeated measures (MMRM) analysis to assess data from all visits simultaneously. The model will include fixed effects for treatment, age group (pediatric, adult), visit and treatment by-visit interaction, with visit as the repeating factor and patient as a random effect, and baseline PKAN-ADL total score as a covariate. The PKAN-ADL total score obtained prior to the first dose of investigational product will serve as each patient's baseline value.

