Patients with PKAN-ADL administration errors will be included in the Double-Blind FAS, but excluded from the PPS, as per [Section 4.5](#). Imputation rules for the data affected by the translation issue can be found in [Section 4.1](#).

The linear mixed-effect model will be implemented using PROC MIXED in SAS with the restricted maximum likelihood (REML) estimation method. An unstructured variance-covariance matrix will be used to model the within-patient errors. [Note: In the unlikely event that the computational algorithm fails to converge, the following structures will be executed in the order specified (essentially in decreasing order of complexity) until convergence is achieved: Toeplitz with heterogeneity, autoregressive with heterogeneity by Week, compound symmetry with heterogeneous variances by Week, autoregressive, Toeplitz, and compound symmetry without heterogeneous variances by Week.]

Significance tests will be based on least squares means (LSMs) using Type III sum of squares. The Kenward and Roger method will be used for calculating the denominator degrees of freedom for tests of fixed effects.

The PROC MIXED SAS coding is as follows:

```
proc mixed data=DATA;
    class TRT WEEK PATIENT;
    model C_score = BASE_score AGE TRT WEEK TRT*WEEK / solution
    ddfm=kr;
    repeated WEEK / subject=PATIENT type=un;

run;

where:
    TRT = treatment group (0 = placebo, 1 = fosmetpantotenate)
    WEEK = week 3, 6, 12, 18, 24
    AGE = age group (0=Pediatric, 1= Adult)
    C_score = change in score from baseline
    BASE_score = baseline score
```

The LSMS for each treatment, the difference between the LSMSs, and the standard error (SE) and 95% confidence interval (CI) associated with the difference will be reported at each study visit. The primary treatment comparison will be based on the test of contrast between treatment effects using the LSM estimate at Week 24, adjusted for baseline score and age group from the Type III analysis.

To estimate the mean change from baseline for PKAN-ADL total scores in each treatment group (placebo or fosmetpantotenate) at Week i ($i = 3, 6, 12, 18$, and 24), the following estimate statement (as an example) will be utilized:

```
estimate 'Placebo Group at Week 24'
    intercept 1
    AGE        <proportion in age group=0  proportion in age group=1>
    BASE_score <mean of BASE_score>
    TRT        1 0
    WEEK       0 0 0 0 1
    TRT*WEEK   0 0 0 0 1
                0 0 0 0 0 / cl;

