4.10.1.1 Sensitivity Analysis

To check that primary efficacy findings are robust, sensitivity analyses will be performed, as follows:

- The MMRM described in [section 4.10.1](#) will be repeated using the PPS, and presented in a similar manner. Of note, patients who had a PKAN-ADL administration error will be excluded from the PPS.
- In addition, analysis of covariance (ANCOVA) models will be applied to change from baseline in PKAN-ADL total scores assessed after 3, 6, 12, 18, and 24 weeks of treatment. For each week analyzed, the model will include treatment and age group (pediatric, adult) as fixed effects, and baseline PKAN-ADL total score as a covariate.

The ANCOVA analysis will be performed for the Double-Blind FAS using PROC GLM in SAS. The models will be run using the observed case (OC) and last-observation-carried-forward (LOCF) procedure to account for incomplete data. In each case, estimates of adjusted treatment means and the adjusted mean difference between treatment groups will be presented at each time point, along with the two-sided 95% CIs and p-values for treatment comparisons.

The LOCF procedure will be applied for post-baseline observations of the PKAN-ADL total score in which more than 20% of the items are missing and cannot be imputed in the manner described in [Section 4.1](#). The last observed post-baseline PKAN-ADL total score, including those from unscheduled visits, will be imputed to replace the missing value of PKAN-ADL total score.

The PROC GLM SAS coding, to be run for each visit and each OC/LOCF procedure, is as follows:

```
proc glm data=DATA;  
    class TRT AGE;  
    model week_x_total=base_score TRT AGE / solution;  
    lsmeans TRT/ pdiff stderr;
```

run;

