4.10.1.3 Exploratory Subgroup Analysis

The influence of potential prognostic factors on the primary efficacy endpoint will be assessed via the mixed model described for the primary analysis, using the Double-Blind FAS. That is, the mixed model will include baseline PKAN-ADL total score and additional prognostic factors (each considered univariately) as covariates, with treatment group, Week, treatment*Week, and treatment*prognostic factor as fixed effects. The factors to be assessed are as follows:

- Age at screening (pediatric, adult)
- Age at disease onset ($<\text{median}$, $\geq \text{median}$)
- Sex (male, female)
- Baseline PKAN-ADL total score (1st quartile, 2nd quartile, 3rd quartile, 4th quartile).
- Duration of Illness ($<\text{median}$, $\geq \text{median}$)

Factors found to have a significant effect on response ($p < 0.10$) will be examined further, to understand the relationship between prognostic factor and response. For all factors, the

LSMs for each treatment, the difference between the LSMs, and the standard error (SE) and 95% confidence interval (CI) associated with the difference will be reported at each study visit, using the MMRM which includes the given factor as a covariate.

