4.10.2 Secondary Efficacy Endpoint

Part III of the UPDRS consists of 27 items, which correspond to 14 domains related to motor abilities such as tremor, stability, and bradykinesia. Each item has responses ranging from 0-4, with a higher value indicating greater disability. To compute the UPDRS Part III total score, responses are summed across the 27 items, and accordingly, will range from 0-108. For domain totals, responses will be summed across all of the items in a given domain (when domain corresponds to multiple items).

For analysis purposes, data from the pediatric and adult age groups will be pooled. All descriptive summary tables will be repeated using age group as a subgroup.

Descriptive statistics will be presented for the UPDRS Part III total score, with absolute and percent change from baseline, by treatment group for each visit of the double-blind period. For post-baseline assessments, categories for change from baseline UPDRS Part III total score (e.g., >0 , $=0$, <0 , ≤ -1 , ≤ -2 , ≤ -3 , ≤ -4), categories for percent improvement (i.e., decrease) in UPDRS Part III total score from baseline (i.e., $<0\%$, $=0\%$, $>0\%$, $\geq 10\%$, $\geq 20\%$, $\geq 30\%$, $\geq 40\%$, $\geq 50\%$), and categories for UPDRS Part III total score status (improvement, no change, or worsening) will be presented. These categories may be adjusted in a way that ensures that the categories contain at least 10% of patients. This will be run using the Double-Blind FAS and repeated using the PPS, as a sensitivity analysis.

Frequency tables will display change from baseline for each of the 14 domains, by treatment group for each visit of the double-blind period, using categories for change from baseline domain score (i.e., >0 , $=0$, <0 , ≤ -1 , ≤ -2 , ≤ -3), and categories for domain score status (improvement, no change, or worsening). These summaries will be run using the Double-Blind FAS and repeated using the PPS, as a sensitivity analysis.

The MMRM model described above for the primary efficacy endpoint will also be performed for the secondary efficacy endpoint: change from baseline UPDRS Part III total score. The LSMs for each treatment, the difference between the LSMs, and the standard error (SE) and 95% confidence interval (CI) associated with the difference will be reported at each study visit. The analysis will be based on the Double-Blind FAS, and will be repeated using the PPS, as a sensitivity analysis.

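### Randomisation is stratified by weight and age group, but weight is left out of every planned efficacy model without a stated reason

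*SAP*

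**What the plan says.** Both documents name two stratification factors. Protocol 8.5 says "Randomization will be stratified by weight", with bands of at least 40 kg, 20 to under 40 kg and under 20 kg, and adds age group. SAP section 3 agrees: "randomization will be stratified by screening weight and age group (pediatric, adult".

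The efficacy models carry only age group:

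- Protocol 12.9.1, primary MMRM: "The model will include fixed effects for treatment, age stratum (6 to <18 or 18 to 65 years), visit and treatment by-visit interaction", with baseline score as covariate. The synopsis has the same terms.
- SAP 4.10.1, text: "The model will include fixed effects for treatment, age group (pediatric, adult), visit and treatment by-visit interaction". The code matches: "model C_score = BASE_score AGE TRT WEEK TRT*WEEK / solution".
- SAP 4.10.1.1: the same MMRM is repeated on the per-protocol set. For the observed-case and LOCF ANCOVAs, "the model will include treatment and age group (pediatric, adult) as fixed effects", with baseline score.
- SAP 4.10.1.2: the tipping-point analysis uses the primary analytic model.
- SAP 4.10.1.3: the subgroup models take "additional prognostic factors (each considered univariately) as covariates". The factors are age at screening, age at onset, sex, baseline score and duration of illness.
- SAP 4.10.2: "The MMRM model described above for the primary efficacy endpoint will also be performed for the secondary efficacy endpoint".

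Elsewhere weight serves as a demographic variable, a safety measure and the criterion for the paediatric dose. Neither document explains its absence from the efficacy models.

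**The concern.** Stratifying on a factor balances it between arms, so the treatment estimate varies less from trial to trial if that factor is prognostic. A model without the factor leaves its variance in the residual. The reported standard error then ignores the gain: the interval is too wide and the test is conservative.

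The plan follows this principle for age, which Protocol 12.9.1 explicitly treats as a stratum, and drops the other stratum without comment. Because no sensitivity or subgroup analysis includes weight, nothing in the planned output would show whether it matters. At stake is precision in a trial sized for 74 evaluable patients. A weight-adjusted model introduced after unblinding would be post hoc.

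A separate, lower-priority mismatch concerns the tests of improvement, no change and worsening. The SAP uses an unstratified chi-squared test for PKAN-ADL (4.10.1), UPDRS Part III (4.10.2), CGI-I at Week 24 (4.10.3.1), BAD (4.10.3.2), Neuro-QoL (4.10.3.3.1), EQ-5D index (4.10.3.3.2) and FIM (4.10.3.4). Protocol 12.9.1 and, for exploratory endpoints, SAP 4.10.3 call for Cochran-Mantel-Haenszel (CMH) methods stratified by age group. The protocol synopsis asks only for chi-square methods. These tests lie outside the gatekeeping sequence in SAP 4.10.4.

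**Working it through.** **1. The plan's own figure.** Inputs from SAP 4.2: 37 per arm, difference 3, SD 4.5, two-sided alpha 0.05, Student's t-test. The standard error is 4.5 × √(2/37) = 1.046 and the noncentrality is 3/1.046 = 2.87 on 72 df, giving power of 80.8%. The stated figure of about 80% reproduces. It comes from an unadjusted test, so it does not depend on whether weight is in the model.

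**2. Effect on interval width.** Let R² be the share of residual variance, after age group and baseline score, that weight explains. The documents give no value, so 0%, 5%, 10% and 20% are assumed. A model without weight reports a standard error near 4.5 × √(2/37); the stratified design and a model with weight give about √(1 − R²) times that. The ratio of interval widths is therefore about 1/√(1 − R²):

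- R² = 5%: 1/√0.95 = 1.026
- R² = 10%: 1/√0.90 = 1.054
- R² = 20%: 1/√0.80 = 1.118

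**3. Simulation.** Week 24 ANCOVA, N = 74, effect 3, residual SD 4.5 after age and baseline, permuted blocks of 4 within four strata, 12,000 runs per cell. Assumed mixes of adult / paediatric ≥40 / 20 to <40 / <20 kg were 60/20/16/4%, 50/22/23/5% and 40/25/28/7%. The model without weight has treatment, age group and baseline; the other adds weight as <40 versus ≥40 kg. Ranges are over the three mixes.

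| R² | Type I error without weight | Power without | Power with | Power forgone (points) | CI wider by |
|---|---|---|---|---|---|
| 0% | 4.8–5.0% | 79.3–80.3% | 79.4–80.2% | about 0 | about 0% |
| 5% | 4.2–4.8% | 80.5–80.6% | 81.8–81.9% | 1.2–1.4 | 2.5% |
| 10% | 3.9–4.1% | 81.1–81.7% | 83.9–84.3% | 2.6–3.0 | 5.4% |
| 20% | 2.9–3.0% | 81.9–82.7% | 87.7–88.5% | 5.4–6.0 | 12% |

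With weight in the model, type I error stays at 4.8–5.3%. Without it, the mean reported standard error is 1.05 throughout, while the true SD of the estimate is 1.03–1.04, 1.00–1.01 and 0.95–0.97 at R² of 5%, 10% and 20%. Monte Carlo error is about 0.4 points for power and 0.2 for type I error.

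**4. A second set-up.** Weight was entered at three levels (2 df), with half the patients paediatric and a different assumed mix, including 10% of adults at 20 to <40 kg. Type I error without weight was 4.7%, 4.5%, 3.9% and 3.0% at R² of 0%, 5%, 10% and 20%. Power without versus with weight was 81.0/80.7%, 80.9/82.1%, 82.1/84.7% and 83.1/88.6%. The conclusion is the same, and the extra degrees of freedom cost nothing detectable.

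**5. How plausible the R² values are.** Suppose half the sample is paediatric and nearly all adults weigh at least 40 kg (both assumed). The variance explained by weight then lies in the paediatric half, so its share of paediatric variance is 2R²/(1 + R²): 0.10/1.05 = 10%, 0.20/1.10 = 18% and 0.40/1.20 = 33% for R² of 5%, 10% and 20%. The 20% row is best read as the top of the range.

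**The case against.** The strongest reply is that the omission is harmless in direction and of unknown size. The treatment estimate is unbiased, the test errs on the safe side, and the protocol and SAP agree on the covariates. No evidence in the documents says that weight predicts PKAN-ADL change, and much of its information may be confined to children. All of this stands and limits the weight of the point.

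The simulation settings can also be challenged. SAP 4.2 gives 4.5 as the SD of change scores, whereas the simulation uses it as the residual SD after age and baseline. The full analysis set could approach 82 patients rather than 74, and the planned analysis is an MMRM, not a single-visit ANCOVA. If N = 82 and baseline and age are assumed to explain 20% of the variance (residual SD 4.5 × √0.80 = 4.02), the power forgone falls to about 0.2, 0.8 and 1.3 points at R² of 2%, 5% and 10%, from a base of 91–93%. The power figures are therefore illustrative. The width ratio 1/√(1 − R²) depends on neither the SD nor N, so the loss of precision remains.

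Finally, changing the primary model of a pivotal trial may seem heavy for a gain that could be zero, and pooling two weight bands still does not reproduce the strata exactly. The lighter option below answers the first objection. Pooling is a practical choice, because Protocol 6.5.1 expects few children below 20 kg.

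**Conclusion.** The concern holds. Weight is a stratification factor, no planned efficacy analysis includes it, and no reason is given. The consequence is a possible loss of precision, not a threat to validity: type I error is at or below nominal and the planned power stands. If weight explains 5–10% of the residual variance, the interval is about 2.5–5.4% wider than necessary and about 1 to 3 points of power are forgone under the 74-patient settings; at 20%, about 12% and 5 to 6 points. If it explains none, nothing is lost either way. These sizes rest on assumed values for R², the age and weight mix, the block size and a single-visit model. The change is worth making because it costs little and the information is already held.

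**What to change.** Before unblinding, add the IWRS weight stratum as a fixed effect to the primary and secondary MMRMs and to the ANCOVAs. Fix the pooling now at two levels, at least 40 kg and under 40 kg. Make matching edits to the CLASS, MODEL and ESTIMATE statements, to the hypothesis wording in SAP 4.10.1 that names the adjustment factors, and to the model description in the protocol synopsis and 12.9.1. The cost is one model degree of freedom, no new data, a SAP revision and a protocol amendment under Protocol 13.3.

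If the sponsor keeps the current primary model, the SAP should state why weight is omitted and pre-specify one sensitivity MMRM with the two-level weight term. That needs SAP wording only.

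Separately, replace the unstratified chi-squared tests of improvement, no change and worsening, at all seven places listed above, with the age-stratified CMH test. The row-mean-score form already planned for the seven-point CGI-I ratings suits these ordered categories.

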9.2. Demographic and Screening Assessments

Approximately 82 patients will be enrolled in the study. The nature of this study and the potential risks associated with participation in the study will be explained to all potential study patients and their parent/legal guardian as appropriate. Written informed consent/assent will be obtained before any screening procedures are performed.

Demographic data will include age, race, ethnicity, and gender. Complete medical history, including a detailed history of PKAN on the PKAN-specific Medical History form, will be obtained, along with concomitant medications/therapies at enrollment.

Patients who are re-screened due to initial screening failure will undergo confirmation of inclusion and exclusion criteria, assessment of PKAN-ADL, UPDRS Part III, and any other necessary assessments (see [Section 6.2](#)).

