4.1 General Statistical Considerations

Tabulations of summary statistics, graphical presentations, and statistical analyses will be performed using SAS® Version 9.3 or higher. All data collected will be summarized using descriptive statistics, including mean, standard deviation (SD), median, minimum, and maximum for continuous variables, and frequency tables with counts and percentages for categorical variables. Age group categorization will be consistent with the Protocol Version that was applicable at time of patient randomization.

Unless otherwise stated, the “baseline” assessment for the double-blind period will be defined as the last measurement obtained prior to the first dose of blinded investigational product (pre-dose on Day 1). For patients who enter the open-label extension period, the baseline value will be re-defined for the open-label period as the last observation prior to start of open-label fosmetpantotenate, unless otherwise specified.

As appropriate, the scales used as efficacy endpoints to measure neurological impairment, dystonia, motor function, and quality of life will be scored and/or normalized in accordance with user manuals and published scoring procedures for each instrument. For each scale, the prescribed rules for deriving the total score in the presence of 1 or more missing items will be followed.

Unless otherwise noted, if at least 80% of the items for a scale (i.e., PKAN-ADL, UPDRS Part III, BAD, Neuro-QOL) are non-missing, then the prorated total score for the scale is obtained by summing the non-missing item responses, multiplying by the total number of items in the scale, and then dividing by the number of non-missing items.

There are two patients who had a question (item) on the PKAN-ADL mistranslated for screening and baseline visits. In analyses using the Double-Blind Full Analysis Set, the values for this item will be rendered invalid, set to missing, and the PKAN-ADL total score will be prorated as described above. The invalid values will be presented and flagged in the data listing, as originally recorded.

For by-visit summaries, the last non-missing assessment (including repeat assessments, if any) recorded at each visit will be used for summarization. For across visit summaries (e.g. maximum post-baseline value), scheduled, unscheduled (if any) and repeat assessments will all be considered for the value to be analyzed; all observations will be presented in data listings.

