4.2 Determination of Sample Size

It is estimated that a total of 74 patients (37 in each treatment group) will provide approximately 80% power to detect a 3-point difference between groups in the average change from baseline score for the PKAN-ADL, based on Student's t-test with alpha=0.05 (two-sided); this calculation assumes a standard deviation of 4.5 points for the change from baseline scores. Allowing for 10% attrition, a total of 82 patients will be randomized to achieve the target sample size of at least 74 patients completing the double-blind period of the study.

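### Efficiency point: the primary model adjusts for one pre-dose PKAN-ADL score, although a Screening score is also scheduled before randomisation and could add some precision at almost no cost

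*SAP*

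**What the plan says.** SAP 4.10.1 describes the primary MMRM as having treatment, age group, visit and treatment-by-visit effects, "with visit as the repeating factor and patient as a random effect, and baseline PKAN-ADL total score as a covariate". The SAS code has the same covariates: "model C_score = BASE_score AGE TRT WEEK TRT*WEEK / solution". Baseline is the last score before the first blinded dose (SAP 4.1), normally the Day -1 visit. Protocol 12.9.1 gives the same covariates.

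Table 15.1-1 of the protocol schedules the PKAN-ADL and UPDRS Part III at Screening (Days -29 to -2) and again at Baseline (Day -1). Entry requires a PKAN-ADL score of at least 6 (Protocol 7.1). Protocol 9.2 repeats both scales on re-screening: "Patients who are re-screened due to initial screening failure will undergo confirmation of inclusion and exclusion criteria, assessment of PKAN-ADL, UPDRS Part III". SAP 4.1 confirms that scores are recorded at both visits: "There are two patients who had a question (item) on the PKAN-ADL mistranslated for screening and baseline visits".

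The Screening score enters none of the planned models: the MMRM, the ANCOVA (SAP 4.10.1.1), the imputation regression (SAP 4.10.1.2) or the UPDRS Part III models (SAP 4.10.2).

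On sample size, SAP 4.2 states that "a total of 74 patients (37 in each treatment group) will provide approximately 80% power to detect a 3-point difference between groups", and "this calculation assumes a standard deviation of 4.5 points for the change from baseline scores".

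**The concern.** A single clinical rating mixes the patient's true severity with visit-to-visit rating noise. A second rating taken up to about four weeks earlier helps separate the two, so together they may predict the Week 24 score better than the Day -1 score alone. Both precede randomisation, so using both cannot bias the comparison and leaves the outcome, change from Day -1, as it is.

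At stake is the width of the confidence interval on the one test that also gates the secondary endpoint (SAP 4.10.4). The protocol's introduction puts prevalence at 1 to 3 per million, and the design has little power to spare, so even a small gain from data already collected deserves consideration.

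**Working it through.** **1. The plan's own figure.** Inputs from SAP 4.2: 37 per arm, difference 3, SD 4.5, two-sided alpha 0.05. The standard error is 4.5 × √(2/37) = 1.046, so the noncentrality is 3/1.046 = 2.87. With 72 degrees of freedom, noncentral-t power is 80.8%. The stated figure of about 80% is reproduced.

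**2. Cost if Screening adds nothing.** With the residual SD kept at 4.5, going from 70 degrees of freedom (intercept, treatment, age group and one baseline fitted) to 69 moves power from 80.73% to 80.71%.

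**3. Gain if it helps.** Two inputs are assumptions, because the documents give neither: the short-term reliability R of a PKAN-ADL total, and its baseline SD s. The SD of change is held at 4.5.

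- True change variance over 24 weeks: VD = 4.5² − 2(1−R)s².
- Week 24 residual variance given Day -1 alone: V1 = s² + VD − R²s².
- Reduction from adding Screening, with no true change between Screening and Day -1: R²s²(1−R)/(1+R).

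Middle case, R = 0.95 and s = 7: VD = 20.25 − 4.90 = 15.35. V1 = 49 + 15.35 − 44.22 = 20.13. The reduction is 0.9025 × 49 × 0.05/1.95 = 1.13, leaving 18.99, a cut of 5.6%.

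| R, s | Day -1 only | Plus Screening | Cut | Power (70 → 69 df) | Patients for the same precision as 74 |
|---|---|---|---|---|---|
| 0.98, 6 | 20.24 | 19.89 | 1.7% | 80.8% → 81.4% | 73 |
| 0.95, 7 | 20.13 | 18.99 | 5.6% | 81.0% → 83.1% | 70 |
| 0.90, 8 | 19.61 | 16.88 | 13.9% | 82.0% → 87.2% | 64 |

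**4. Allowing for drift.** Step 3 assumes that Screening predicts Week 24 as well as Day -1 does. Suppose instead that the true score drifts as a random walk with variance q = VD/24 per week, and that Screening falls g weeks before Day -1. Then Cov(S, Day -1) = Cov(S, Week 24) = c = Rs² − qg, and Var(S) = s² − qg. The reduction becomes [c(1−R)]² / [Var(S) − c²/s²].

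Middle case, g = 4: qg = 4 × 15.35/24 = 2.56, c = 43.99 and Var(S) = 46.44. The reduction is 2.20²/(46.44 − 39.49) = 0.70, leaving 19.43, a cut of 3.5%.

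For gaps of 1 to 4 weeks:

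- R = 0.95, s = 7: cut of 4.9% to 3.5%, power 82.8% to 82.3%.
- R = 0.98, s = 6: cut of about 1% to 0.5%.
- R = 0.90, s = 8: cut of 13.5% to 12.3%.

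Under this drift the best slopes on the two pre-dose scores are the same at every post-baseline visit. The SAP's common-slope MMRM, with complete data, therefore gives the same Week 24 variance as the single-visit calculation. Other patterns of drift would move these figures.

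**5. When the gain is zero.** Screening adds nothing when its correlation with Week 24 equals the product of the Screening–Day -1 and Day -1–Week 24 correlations. Take a baseline SD of 9. The Day -1–Week 24 correlation is then 1 − 20.25/(2 × 81) = 0.875. With a Screening–Day -1 correlation of 0.95, the variance cut is 8.4% if Screening also correlates 0.875 with Week 24, 2.5% at 0.855, and zero at 0.95 × 0.875 = 0.831.

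**The case against.** The strongest reply is that nothing is wrong with the plan. Adjusting for the last pre-dose score and age group is valid and prespecified, and the stated power reproduces. That stands.

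Second, every input that sets the size of the gain is assumed. The larger figures need Screening to predict Week 24 as well as Day -1 does, in a disease the protocol calls progressive and with a gap of up to about four weeks. That also stands, and it is why the range must start at zero. Age group may already explain a little of the same variance, the entry cut-off of 6 truncates the score, and the mistranslated item affects both visits in two patients. Each could trim the gain slightly; none could bias the contrast.

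Third, the edit reaches beyond one sentence. The covariate set appears in the hypotheses, the model code, the sensitivity analyses and the protocol, and a Screening total that cannot be prorated could drop a patient from the model. That is right, and the fix has to deal with it.

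A reader might infer that the primary analysis is flawed, that the trial is underpowered, or that a definite number of patients' worth of information is being lost. The documents support none of these. The test is valid at its stated power, and no document gives the baseline SD or test-retest correlation needed to fix the loss.

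**Conclusion.** The point holds as a free improvement in efficiency, not as a correction of an error. A pre-randomisation PKAN-ADL is scheduled for every patient and left out of every model. Under assumed reliability 0.90 to 0.98 and baseline SD 6 to 8, using it would cut the Week 24 residual variance by about 0.5% to 14%. The middle case is about 3.5% to 5.6%, with power rising from 81% to about 82–83%; in patients, 74 × 0.965 = 71 to 74 × 0.944 = 70 would give the precision of 74. The gain falls to zero if Day -1 carries all the information, and the loss is then 0.02 of a power point. The case for the change rests on that asymmetry and not on any one figure for the gain.

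**What to change.** Before database lock and unblinding:

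- Keep change from the Day -1 baseline as the outcome. Add the last qualifying Screening PKAN-ADL total as a second covariate in the primary MMRM, the OC and LOCF ANCOVA, and the analytic model of the tipping-point analysis. Include it in the imputation regression too, so that the imputation and analysis models agree.
- Apply the 80% item rule of SAP 4.1 to the Screening total. If it still cannot be computed, substitute the Day -1 total, so that no FAS patient is dropped.
- Do the same with the Screening UPDRS Part III total in the secondary models.
- Update the hypothesis text, the MODEL statements and the group-mean ESTIMATE statements (which need the mean Screening score). The treatment-difference ESTIMATE statement is unchanged.
- State whether the subgroup models in SAP 4.10.1.3 follow, and document the departure from Protocol 12.9.1 and the synopsis.

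The cost is one degree of freedom and edits in several places. No new data are needed.
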